5.3 PER PROTOCOL POPULATION

The Per Protocol Population will include all subjects in the mITT Population with no major protocol violations. Major protocol violation criteria (defined as CSR reportable violations) have been established (prior to database lock) and included in the Protocol Deviation Plan. These protocol violations will be presented in the Clinical Study Report. Efficacy analyses may also be performed based on the Per Protocol Population.

5.4 SAFETY POPULATION

The Safety Population will include all subjects who have received any dose of study medication. Analyses based on this population will group subjects according to the treatment they received rather than the treatment they were randomized to receive. All safety analyses will use the Safety Population.

In the primary safety summaries, data for Sites 068 and 077 mentioned in [Section 5.2](#) will be excluded, due to an inability to verify compliance with adverse event reporting requirements, leading to possible under-reporting of adverse events. However, supportive safety summaries will include the data from Sites 068 and 077.

6. GENERAL CONVENTIONS

Unless otherwise stated, all analyses will be performed using SAS Version 9.2, and all hypothesis tests will be conducted at a two-sided significance level of 0.05. P-values will be presented with 3 decimal places, and p-values that are less than 0.001 will be presented as <0.001.

Continuous (non-survival-related) data will be summarized using descriptive statistics: number of observations (n), mean, standard deviation (SD), median, minimum and maximum. Frequencies and percentages will be used to summarize categorical (discrete) data. Presentations of categorical data will generally suppress percentages for items where the count is zero, in order to draw attention to the nonzero counts. In general, mean, SD, median, minimum, maximum and percentages will be presented with one decimal place.

Unless otherwise stated, confidence intervals, when presented, will be constructed at the two-sided 95% level. For binomial variables, the 95% confidence intervals will be constructed using the normal approximation without continuity correction.

Data listings will present all data collected on Case Report Forms (CRFs) by study drug, center and subject number. Unless otherwise stated, data will be presented by treatment and overall.

6.1 DEFINITION OF BASELINE

Unless otherwise stated, the randomization baseline will be defined as the last assessment recorded on the day of randomization (e.g., weekly average in pain intensity).

Open-label titration pain score baseline is defined as a single assessment prior to entering the Open-Label Titration Phase.

Analyses will be conducted using SAS Version 9.2 or higher.

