¹² IR morphine (15 mg QID for subjects with screening MED of ≥80 mg/day; or 15 mg TID for subjects with screening MED between 40 mg and 79 mg/day) for at least 2 days prior to Day 1 of the Titration Phase. A 12-hour washout from the last IR morphine dose is required before the Buprenex test dose is given.

¹³ One IM injection of 0.3 mg (1.0 mL) Buprenex.

¹⁴ COWS/SOWS will be assessed before the test dose, 15 min (allowable window of between 15-30 minutes) after the test dose, and 24 hours (allowable window of ±3 hour) after the first 4 mg or 8 mg CAM2038 dose. If COWS score is not ≥5, the COWS can be repeated for up to 48 hours.

¹⁵ The first dose of either 4 mg or 8 mg CAM2038 q1w will be administered within 4 hours (+30 minutes) after the test dose. During the first week of the Titration Phase, subjects who experience significant pain may, at the discretion of the investigator, receive an additional CAM2038 at their respective dose (4mg or 8 mg) on Day 3, 4 or 5. Dose adjustments will be made by increasing or decreasing the dose level of CAM2038 q1w at the scheduled weekly visits (doses of 4 mg, 8 mg, 12 mg, 16 mg, 24 mg, or 32 mg per week). Subjects who require doses >32 mg/week will be discontinued from the study.

¹⁶ Electronic diary dispensed after test dose.

¹⁷ ‘Screening’ version at Screening and ‘Since Last Visit’ version every other week during the Titration Phase.

¹⁸ Any spontaneously reported AEs will be recorded after the subject signs the ICF. In addition, AEs will be elicited using a non-leading question each time the subject visits the clinic.

Table 6: Schedule of Assessments for Subjects Randomized to Once Weekly Injections

Study Period/Phase:	Double-Blind Phase ^{ab}												Final Study Visit ^c	Follow-up Phase ^d		
	Month:	M4				M5				M6					M7	
	Week:	11	12	13	14	15	16	17	18	19	20	21			22	23
Eligibility Criteria Review	X ^e															
Physical Examination ^f													X			
Vital Signs ^g	X	X	X	X	X	X	X	X	X	X	X	X	X	X		
ECG	X ^h	X			X				X				X			
Clinical Laboratory Assessments	X												X			
Pregnancy Test ⁱ	X	X	X	X	X	X	X	X	X	X	X	X	X	X		
COWS/SOWS ^j	X	X														
CAM2038/placebo q1w SC Injection ^k	X	X	X	X	X	X	X	X	X	X	X	X				
Injection Site Examination	X	X	X	X	X	X	X	X	X	X	X	X	X			
Dispense, Collect, and Record Rescue Medications	X	X	X	X	X	X	X	X	X	X	X	X	X ^l			

^a Double-Blind Phase visit window is ±3 days.

^b The first day of the Double-Blind Phase is defined as baseline.

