^c This visit is defined as the twelfth week of the Double-Blind Phase in the analyses of data.

^d Telephone contact only.

^e Prior to enrollment into the Double-Blind Phase, all Inclusion/Exclusion and other relevant criteria must be met.

^f A complete physical examination of all major body systems (including height, weight, and BMI) will be performed.

^g Includes body temperature, blood pressure, pulse rate, pulse oximetry and respiration rate and will be performed at every visit, prior to treatment, and 1-hour post-study treatment (allowable window of 60-90 minutes).

^h ECGs will be assessed at Week 11, prior to treatment and 1-hour post-dose (allowable window of 60-90 minutes).

ⁱ A serum pregnancy test will be performed at the Final Study Visit/Early Termination. An “in-office” urine pregnancy test will be required weekly (for women of childbearing potential).

^j COWS/SOWS will be assessed before dosing.

^k Subjects who are receiving 4 mg, 8 mg or 12 mg CAM2038 q1w will randomize to CAM2038/placebo q1w with weekly injections throughout the Double-Blind Phase.

^l Rescue medication will not be dispensed at this visit.

Study Period/Phase:	Double-Blind Phase ^{ab}												Final Study Visit ^c	Follow-up Phase ^d
Month:	M4				M5				M6					M7
Week:	11	12	13	14	15	16	17	18	19	20	21	22	23	27
Daily Electronic Diary Pain Rating (NRS-11)	X	X	X	X	X	X	X	X	X	X	X	X	X	
EQ-5D-5L	X				X				X				X	
WPAI	X				X				X				X	
C-SSRS ^m	X				X				X				X	
CGI-I Scale	X				X				X				X	
PGI-I Scale	X				X				X				X	
Concomitant Medications/Procedures	X	X	X	X	X	X	X	X	X	X	X	X	X	X
Adverse Events ⁿ	X	X	X	X	X	X	X	X	X	X	X	X	X	X
Adjust Opioid Treatment													X ^o	

BMI=Body Mass Index; CGI-I=Clinical Global Impression Improvement; C-SSRS=Columbia Suicide Severity Rating Scale; COWS=Clinical Opiate Withdrawal Scale; ECG=electrocardiogram; EQ-5D-5L=EuroQoL Group 5-dimension 5-level self-report questionnaire; ET=Early Termination; NRS-11=11-point numerical rating scale; PGI-I=Patient Global Impression of Improvement; q1w=once weekly; q4w=once monthly; SC=subcutaneous; SOWS=Subjective Opiate Withdrawal Scale; WPAI=Work Productivity and Activity Impairment.

^m Since Last Visit' version to be used.

ⁿ Any spontaneously reported AEs will be recorded after the subject signs the ICF. In addition, AEs will be elicited using a non-leading question each time the subject visits the clinic.

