^o At the Final Study Visit (or ET) subjects will be transitioned back to standard care or their treatment prior to study entry.

Table 7: Schedule of Assessments for Subjects Randomized to Once Monthly Injections

Study Period/Phase:	Double-Blind Phase ^{ab}			Final Study Visit ^c	Follow-up Phase ^d
	Month:	M4	M5		
Week:	11	15	19	23	27
Eligibility Criteria Review	X ^e				
Physical Examination ^f				X	
Vital Signs ^g	X	X	X	X	
ECG ^h	X	X	X	X	
Clinical Laboratory Assessments	X			X	
Pregnancy Test ⁱ	X	X	X	X	
COWS/SOWS ^j	X				
CAM2038 q4w/placebo SC Injection ^k	X	X	X		
Injection Site Examination	X	X	X	X	
Dispense, Collect, and Record Rescue Medications	X	X	X	X ^l	
Daily Electronic Diary Pain Rating (NRS-11)	X	X	X	X	
EQ-5D-5L	X	X	X	X	
WPAI	X	X	X	X	

^aDouble-Blind Phase ±7 days

^b The first day of the Double-Blind Phase is defined as baseline.

^c This visit is defined as the twelfth week of the Double-Blind Phase in the analyses of data.

^d Telephone contact only.

^e Prior to enrollment into the Double-Blind Phase, all Inclusion/Exclusion and other relevant criteria must be met.

^f A complete physical examination of all major body systems (including height, weight and BMI) will be performed.

^g Includes body temperature, blood pressure, pulse rate pulse oximetry and respiration rate and will be performed at every visit, prior to treatment, 1-hour post-treatment (allowable window of 60-90 minutes) and at 6-10 hours (t_{max}) after the first CAM2038/placebo q4w dose.

^h ECGs will be assessed at Week 11, prior to treatment and at 6-10 hours (t_{max}) after the first CAM2038/placebo q4w dose.

ⁱ A serum pregnancy test will be performed at the Final Study Visit/Early Termination. An “in-office” urine pregnancy test will be required monthly (for women of childbearing potential).

^j COWS/SOWS will be assessed before dosing and 6-10 hours (t_{max}) after the first dose of CAM2038/placebo q4w.

^k Subjects who are receiving 16, 24, or 32 mg CAM2038 will be randomized to CAM2038/placebo q4w (64, 96, or 128 mg) and receive 3 doses with CAM2038/placebo q4w (Weeks 11, 15 and 19)

^l Rescue medication will not be dispensed at this visit.

Study Period/Phase:	Double-Blind Phase ^{ab}			Final Study Visit ^c	Follow- up Phase ^d
	Month:	M4	M5		
Week:	11	15	19	23	27
C-SSRS ^m	X	X	X	X	
CGI-I Scale	X	X	X	X	
PGI-I Scale	X	X	X	X	
Concomitant Medications/Procedures	X	X	X	X	X
AEs ⁿ	X	X	X	X	X
Adjust Opioid Treatment				X ^o	

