9.2 DERIVATION OF THE PRIMARY EFFICACY VARIABLE

WAAPI scores will be calculated for each weekly interval (i.e., 7-day intervals) relative to randomization date (first randomized treatment date) for all subjects (both subjects on q1w and q4w). For example, WAAPI at Week 0 will be the average of available (non-missing) APIs captured during the 7 days prior to Treatment Day 1 (the first randomized treatment day). WAAPI at Week 1 will be the average for the next 7 days including the score captured on Day 1. WAAPI at Week 12 (the primary timepoint) will be the average for the APIs captured from Day 78 to Day 84. The baseline WAAPI score will be the WAAPI at Week 0. The changes from baseline at any post-baseline timepoint will be calculated as baseline minus post-baseline, so that a positive change is indicative of improvement.

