10.5 PHYSICAL EXAMINATIONS

Number and percent of subjects with abnormal physical exam findings at Screening will be summarized by body system for each treatment group and overall. Physical examinations data for each subject will also be presented in a listing.

10.6 12-LEAD ELECTROCARDIOGRAM (ECG)

Twelve-Lead ECGs will be assessed after the subject has been resting in a recumbent/supine position for at least 3 minutes (see Protocol Section 9.5.11 for a complete list of parameters to be assessed). The ECG variables will include ventricular heart rate and the PR, QRS, QT, QTcB and QTcF intervals. The ECGs

will be signed and dated by a medically qualified individual; he or she will confirm review of the ECG and verify whether any abnormalities are clinically significant.

Number and percent of subjects in each ECG finding category (normal; abnormal not clinically significant; and abnormal and clinically significant) will be summarized for each visit by each treatment group and overall. Summary statistics will be presented for the actual value and change for each ECG parameter.

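### The SAP's default baseline is usually a post-dose reading for vital signs, ECG and (q4w only) COWS/SOWS, because it has no pre-dose condition

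*SAP*

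**What the plan says.** The default rule is in SAP 6.1: unless another definition is given, "the randomization baseline will be defined as the last assessment recorded on the day of randomization". SAP 9.2 counts study weeks "relative to randomization date (first randomized treatment date) for all subjects", so the randomisation date and the first double-blind dosing date are treated as one. The protocol adds only, in a footnote to Tables 6 and 7, that "The first day of the Double-Blind Phase is defined as baseline". Neither document limits baseline to readings taken before the injection.

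The protocol sets these Week 11 readings:

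- **q1w (Table 6):** for ECG, "ECGs will be assessed at Week 11, prior to treatment and 1-hour post-dose". Vital signs follow the same pattern at every visit. COWS/SOWS is taken before dosing only.
- **q4w (Table 7):** for ECG, "ECGs will be assessed at Week 11, prior to treatment and at 6-10 hours" after the first injection, a time the protocol labels tmax. Vital signs are taken before dosing, at 1 hour and at 6-10 hours. COWS/SOWS is taken before dosing and at 6-10 hours.

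Some variables have their own baseline: WAAPI (SAP 9.2, the 7 days before Treatment Day 1), laboratory tests (SAP 10.3) and the endpoints referred to the titration-phase baseline (for example SAP 9.5.2). SAP 10.4 (vital signs), 10.6 (ECG), 10.9 (COWS) and 10.10 (SOWS) give none.

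SAP 10.4 plans change from baseline for vital signs. SAP 10.6 states that "Summary statistics will be presented for the actual value and change for each ECG parameter". For COWS and SOWS the SAP promises only summaries and listings, but Protocol 11.3.7 plans change-from-baseline statistics for them too.

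**The concern.** A baseline should precede the treatment it is used to assess. Here the stated rule selects the latest reading on a day when the protocol deliberately takes readings after the injection. The reading meant to show the early effect of the first double-blind dose can become the reference against which effects are measured.

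QTcF is a declared interest of this protocol, which has entry limits, a check for a rise above 30 ms after the test dose, and attention to post-baseline rises of 60 ms or more (Protocol 7.2, 8.1.3 and 9.5.11). What is at stake is whether the change columns in the double-blind ECG, vital-sign and withdrawal-scale tables mean what a reader will take them to mean.

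**Working it through.** The plan gives no figure to reproduce, so this is a check of rule against schedule, followed by clock arithmetic and a line of algebra.

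**1. Last scheduled reading on the first double-blind day**

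| Variable | q1w | q4w |
|---|---|---|
| Vital signs | 1 to 1.5 h after dose | 6 to 10 h after dose |
| ECG | 1 to 1.5 h after dose | 6 to 10 h after dose |
| COWS/SOWS | before dose | 6 to 10 h after dose |

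Five of the six cells are post-dose. The exception is q1w COWS/SOWS.

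**2. Does the post-dose reading fall on the same date?** A dose at clock time T with a reading d hours later stays on the same date if T + d < 24:00.

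- q1w, d up to 1.5: always, if T is before 24:00 − 1.5 h = 22:30.
- q4w, d from 6 to 10: always, if T is before 24:00 − 10 h = 14:00; possibly, if T is before 24:00 − 6 h = 18:00; never after that.

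When the q4w reading passes midnight, the ECG and COWS/SOWS baselines revert to pre-dose. The vital-sign baseline becomes the 1-hour reading, which is still post-dose. One q4w table could therefore mix two kinds of baseline, sorted by time of injection.

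**3. Effect on a change score.** Let P be the pre-dose reading, P + x the post-dose reading on the same day, and Y a later reading.

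- Change from pre-dose: Y − P.
- Change under SAP 6.1: Y − (P + x) = (Y − P) − x.

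If a fraction p of subjects in each arm has a post-dose baseline, and the mean increments among them are xA (active) and xP (placebo), the active-minus-placebo difference in mean change moves by −p(xA − xP). The documents give no effect size. Purely as an assumption, take xA − xP from 0 to 10 ms with p = 1. The shift is then 0 to −10 ms, and a 5 ms increment gives −5 ms. With p = 0 there is no shift.

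**4. What is left to measure for q4w.** Week 11 is the only time the double-blind schedule places an ECG at 6-10 hours (Table 7 and Protocol 9.5.11). If that ECG is the baseline, its own change is zero by definition. Table 7 marks COWS/SOWS at Week 11 only. If the 6-10 hour score is the baseline, no later scheduled score in that phase remains to compare with it.

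**The case against.** The best defence is that SAP 6.1 was written with pain in mind, since its example is a weekly pain average, and that any programmer would use the pre-dose value. SAP 10.6 does not even name the reference point for its change. But pain has its own rule in SAP 9.2, and the default is worded generally, so it governs whatever has no rule of its own. Quietly using the pre-dose value would depart from a final SAP without a record.

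Three points against the weight of the concern do stand:

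- Every randomised subject has been on a stable CAM2038 q1w dose for at least 2 weeks (Protocol 7.4). The pre-dose reading is not drug-free, and x is only the increment over it.
- Actual values are tabulated for vital signs and ECG, and the protocol promises by-subject listings of all safety data. A post-dose rise stays visible there.
- SAP 10 pre-specifies no safety outcome and treats any formal between-arm safety comparison as post hoc. The affected tables are descriptive.

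A reader might go further and infer that the QTcF and respiratory comparison is biased towards no difference and that a peak effect is wholly erased. The documents do not support this. Only the q4w 6-10 hour reading is labelled tmax; nothing calls the q1w 1-hour reading a peak. The direction depends on whether later readings are pre-dose or post-dose, which SAP 10.4 and 10.6 do not say. Placebo subjects are coming off buprenorphine, so their values may move as well. Only the change scores lose the increment.

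**Conclusion.** The point holds as a defect in a stated rule. If SAP 6.1 is followed as written, the double-blind baseline for vital signs and ECG in both regimens, and for COWS/SOWS under q4w, is usually a post-dose value. Each affected change score is off by that subject's acute increment x, a size the documents do not give. Late q4w dosing makes ECG and COWS/SOWS baselines inconsistent between subjects, and the one planned 6-10 hour q4w ECG cannot show up as a change.

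This rests on reading SAP 6.1 literally, on randomisation and first dose sharing a date (SAP 9.2), and on the Week 11 readings being taken as scheduled. For COWS/SOWS it also rests on Protocol 11.3.7 being the source of the change analysis. The reach is limited to descriptive change-from-baseline safety summaries. The primary analysis, the laboratory summaries and the titration-baseline endpoints are outside it. It should be corrected, but it does not threaten the trial's main conclusion.

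**What to change.** In SAP 6.1 (or in 10.4, 10.6, 10.9 and 10.10), define the double-blind baseline for vital signs, ECG, COWS and SOWS as the last non-missing assessment before the first double-blind injection. Summarise the Week 11 readings at 1 hour and at 6-10 hours as post-baseline time points, and state in 10.4 and 10.6 whether later visits use the pre-dose or the post-dose reading.

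Restrict the new rule to these variables. Applied to everything, it would displace the 7-day WAAPI baseline in 9.2 and the titration-phase baselines, which should stay as they are, along with the laboratory rule in 10.3.

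The cost is one sentence of definition, short additions to the safety sections and table shells, and a 1.0x revision under SAP 6.2. The pre-dose readings are already scheduled, so no new data are needed.

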6.2 CHANGES TO PLANNED ANALYSES

Draft versions of the SAP will be numbered sequentially as Version 0.0x. The final approved version will be numbered as Version 1.00. Revisions after the “Final” version will be numbered as Version 1.0x. The Clinical Study Report will document any changes made after the final approved version before unblinding.

7. DESCRIPTION OF THE STUDY POPULATIONS

All tables, figures and listings must include population descriptors in the titles (e.g., mITT Population, Safety Population, Per Protocol Population).

7.1 DISPOSITION

Subject disposition summaries will be presented by treatment arm and will include the number of subjects randomized, the number and percentage of randomized subjects in the primary Safety, mITT, and Per Protocol (if applicable) Populations, as well as the number and percentage of subjects who complete the study. The summaries will also include the reasons for early discontinuation from the study.

Disposition summaries will be presented for the primary Safety, mITT, and Per Protocol Populations (if applicable) separately.

7.2 DEMOGRAPHIC AND BASELINE CHARACTERISTICS

A summary of demographics and baseline characteristics will be presented by treatment arm and overall for the mITT and the primary Safety Population. The demographic characteristics will consist of age, sex, ethnicity, and race, and will use descriptive statistics.

Demographic data including age, sex, ethnicity, and race, as well as baseline clinical characteristics, will be summarized. Age will be calculated based on the following conditional algorithm:

- Has the subject had his/her birthday this year?
 - Yes; then AGE = (year of informed consent) – (year of birth)
 - No; then AGE = (year of informed consent) – (year of birth) – 1

Since the birth dates capture the months and years only, the days will be imputed as the first day of the month before applying the above rules to derive the ages.

Clinical baseline characteristics summarized will include, at minimum, body mass index, current employment status, duration of low back pain, and pain score at the beginning of the open-label titration phase. Clinical baseline characteristics will be summarized by treatment group and overall.

7.3 MEDICAL HISTORY

Medical history will be coded using the Medical Dictionary of Regulatory Activities (MedDRA). A medical history listing will be presented.

8. PRIOR AND CONCOMITANT MEDICATIONS

All medications recorded on the CRFs will be coded using the WHO Drug Dictionary. Prior and concomitant medications will be summarized by treatment arm in the Safety Population by Anatomical Therapeutic Chemical Class Level 4 and WHO Drug base substance preferred name.

Prior medications are defined as medications with stop dates occurring before the date of first administration of any study medication. Concomitant medications are defined as medications with start dates occurring on or after the date of first administration of any study treatment component and no more than 30 days after the last administration of any study treatment component. Medications with start and stop dates that bracket the date of first administration of any study treatment component will be summarized as both prior and concomitant medications.

Prior and concomitant medication will be summarized for both Primary and Supportive Safety Populations.

9. EFFICACY ANALYSES

Twenty-four hour API, WPI and rescue medication use will be collected daily by electronic diary. Paper diary entries will be collected in situations where electronic diary transmission issues occur and where electronic diaries are unavailable. For cases where both electronic and paper diaries are available, only the data from the electronic source will be used. Pain-related efficacy evaluation will be based on electronic diary data only. Additional sensitivity analyses will be conducted with both electronic and paper diary data as supportive efficacy.

